## **4.4 中心培训，认证**

执行委员会对所有分中心进行了 GCP 培训以及结局评价的培训（例如：NIHSS, mRS）

在研究启动之前，分中心主要研究者和协调员按照要求完成培训并取得认证证书。在这些培训项目中，研究者对患者进行筛选的标准和随访的过程将被评估。在案例研究过程中一些涉及研究方案的潜在问题或模糊不清的内容将被讨论。

所有的研究者必须完成以下的培训并取得证书：

- 研究流程
- TIA 的诊断方法的指导说明
- ABCD2 的使用

- CHANCE 的入组条件
- mRS 评分
- NIHSS 评分
- SSS-TOAST
- EQ-5D
- 终点事件判读
- GUSTO
- 血样亚组的血样收集
- 影像亚组影像学资料收集（DICOM 格式）

每个中心在招募患者之前必须要完成项目培训并获得认证。研究中心 PI 和主要研究成员将定期参加电话会议以解决研究中遇到的问题。认证资格将由 4 个培训中心颁发。

详尽的研究流程手册作为研究者的主要参考文档。它为研究中心的研究者提供培训指导，并在整个研究期间定期地根据需要在 CHANCE 研究网站上进行更新。执行委员会成员与研究协调员将以电话，传真或 e-mail 的形式与中心研究者保持沟通，解决研究中遇到的问题。CHANCE 执行委员会与监督委员会一起回答各分中心遇到或提出的疑问，并将这些疑问和答案整理后分发给所有分中心。并保证这些疑问和答案在 CHANCE 研究网站上可以获得。

执行委员会成员将管理并实地考察分中心，以确保记录在病例报告表中的数据完整性与有效性。在整个试验过程中每个研究中心至少被考察一次，如果研究数据质量有疑问或受试者入组有问题会根据需要增加考察次数。

## **4.5 访视计划**

受试者访视时间包括筛选，随机化，21 天访视，90 天访视。除外，患者出现新神经系统临床症状，可疑事件发生

时将接受访视，包括原缺血事件恶化，出现新的短暂的或持续的神经系统症状。分中心将在事件发生 72 小时内将提交事件判读资料。

## **4.6 结局**

对于终点事件结局的定义在附件 1 已给出

### **4.6.1 主要有效终点**

3 个月内新发血管性事件患者的比例，定义为如下任何事件：

- ◇ 任何卒中事件（缺血性或出血性卒中）

### **4.6.2 次要有效终点**

- 3 个月内的血管性事件患者的比例（卒中，心肌梗死，血管性死亡）
- 3 个月内新发血管性事件患者的比例（缺血性卒中/出血性卒中/TIA/心肌梗死/血管性死亡），将其作为一组评估或分别评估。
- mRS 的改变（连续性）和在 3 个月随访时评分为 0-2 分对比 3-6 分两组百分比的改变（量表见附件 2）
- 进一步的针对有效性探索分析：
  - ◇ 神经功能残损（在 3 个月随访时 NIHSS 评分的改变）（量表见附件 3）；
  - ◇ 生活质量（EQ-5D 量表）（量表见附件 4）
- 也将对有效终点事件进行病因学亚组分层分析（非颅内大动脉狭窄性疾病对比颅内大动脉狭窄性疾病），目标事件（TIA 对比小卒中）分析，年龄分析（<65 岁对比 ≥65 岁）

### **4.6.3 安全性终点事件**

#### **4.6.3.1 临床安全性**

评价临床安全性，如下：

- ◇ 在第 1 天、第 21 天和第 3 个月访视时进行体格检查，包括神经系统评估检查；
- ◇ 基线期后每次访视时收集不良事件信息；
- ◇ 每次访视时测量卧位血压和心率。

#### **4.6.3.2 不良事件的收集**

在本研究期间不需要特殊的实验室检查。然而，如果实验室检查结果异常与研究药物相关或导致需要上报的不良事件，那么要求采取特殊的、恰当的行动（见附件 5）

#### **4.6.3.3 心电图**

在基线期随访（第 1 天）应做心电图

#### **4.6.3.4 安全性终点事件**

##### **4.6.3.4.1 主要安全性终点事件**

- ◇ 严重出血事件发生率 (GUSTO 定义，见附件 6)，包括致命性出血和症状性颅内出血；

##### **4.6.3.4.1 次要安全性终点事件**

- ◇ 3 个月时症状性和非症状性颅内出血的发生率
- ◇ 总体死亡率
- ◇ 研究者报告的不良事件/严重不良事件

## 5 患者筛选

在整个研究期间，100家分中心拟入组5100例TIA或小卒中受试者。在患者招募之前，所有的分中心都必须获得当地伦理委员会的批准，伦理委员会可获取所有研究文档和培训材料。

### 5.3 研究人群

#### 入选标准

- 年龄 $\geq 40$ 岁。
- 急性非致残性缺血性卒中（随机化时NIHSS $\leq 3$ 分），且在症状出现的24小时内可以应用研究药物。症状开始的时间定义为“最后看起来正常的时间”。
- 具有中高危卒中风险（随机化时ABCD评分 $\geq 4$ ）的TIA（局灶性脑或视网膜缺血导致的神经功能障碍，并在24小时内完全消失）患者，且在症状出现的24小时内可以应用研究药物。症状开始的时间定义为“最后看起来正常的时间”。
- 已签署知情同意书。

#### 排除标准

- 根据基线头CT或MRI诊断为出血或其他病理性脑疾患，例如血管畸形、肿瘤、脓肿或其他常见的非缺血性脑疾病（例如多发性硬化）。
- 仅存在单独的感觉症状（如麻木感），单独的视力改变，单独的头晕或眩晕，但基线头CT或MRI没有急性梗死证据。
- 随机化时mRS $> 2$ 分（发病前的病史评估）。
- 随机化时NIHSS $\geq 4$ 分。

- 具有明确的抗凝治疗指征（怀疑存在心源性栓塞，如房颤、已知的人工心脏瓣膜、可疑的心内膜炎等）。
- 存在使用氯吡格雷或阿司匹林的禁忌症：
  - 已知过敏史；
  - 严重的肝功能不全或肾功能不全；
  - 严重的心功能衰竭、哮喘；
  - 存在凝血障碍、系统性出血；
  - 既往凝血障碍或系统性出血病史；
  - 既往血小板减少或中性粒细胞减少病史；
  - 既往有药物引起的血液系统疾病或肝功能异常史；
  - 白细胞减少 ( $<2 \times 10^9/l$ ) 或血小板减少 ( $<100 \times 10^9/l$ )；
  - 随机化前 24 小时内使用过溶栓药物。
- 颅内出血病史
- 预计需要长期服用非研究性抗血小板聚集药物，或影响血小板功能的非甾体类抗炎药物。
- 随机化前十天内使用过肝素或口服抗凝药物。
- 随机化前三个月内有胃肠道出血或大手术。
- 随机化后三个月内计划或很可能行血管成形术或血管外科手术。
- 计划中的其他外科手术或介入性治疗可能需要终止服用试验药物。

- 血管成形术或血管外科手术导致的 TIA 或小卒中。
- 患有严重非心血管疾病，预期生存时间小于 3 个月的患者。
- 没有采取有效的避孕措施且妊娠试验阳性记录的育龄期女性。
- 正在接受试验性药物或仪器试验的患者。

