### **5.2 Study Population**

#### Inclusion Criteria

- Adult subjects (male or female  $\geq 40$  years)
- Acute non-disabling ischemic stroke (NIHSS  $\leq 3$  at the time of randomization) that can be treated with study drug within 24 hours of symptoms onset. Symptom onset is defined by the “last seen normal” principle.
- TIA (Neurological deficit attributed to focal brain ischemia, with resolution of the

deficit within 24 hours of symptom onset), that can be treated with study drug within 24 hours of symptoms onset and with moderate-to-high risk of stroke recurrence (ABCD2 score  $\geq 4$  at the time of randomization). Symptom onset is defined by the “last see normal” principle.

- Informed consent signed

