#### Exclusion Criteria

- Diagnosis of hemorrhage or other pathology, such as vascular malformation, tumor, abscess or other major non-ischemic brain disease (e.g., multiple sclerosis) on baseline head CT or MRI.
- Isolated or pure sensory symptoms (e.g., numbness), isolated visual changes, or isolated dizziness/vertigo without evidence of acute infarction on baseline head CT or MRI.
- Modified Rankin Scale Score  $> 2$  at randomization (pre-morbid historical assessment)
- NIH Stroke Score  $\geq 4$  at randomization
- Clear indication for anticoagulation (presumed cardiac source of embolus, e.g., atrial fibrillation, prosthetic cardiac valves known or suspected endocarditis).
- Contraindication to clopidogrel or ASA.
  - Known allergy
  - Severe renal or hepatic insufficiency
  - Severe cardiac failure, asthma
  - Hemostatic disorder or systemic bleeding
  - History of hemostatic disorder or systemic bleeding
  - History of thrombocytopenia or neutropenia
  - History of drug-induced hematologic or hepatic abnormalities
  - Low white blood cell ( $<2 \times 10^9/l$ ) or platelet count ( $<100 \times 10^9/l$ ).

- Use of thrombolysis within 24 hours prior to randomization
- History of intracranial hemorrhage.
- Anticipated requirement for long-term non-study antiplatelet drugs, or NSAIDs affecting platelet function.
- Current treatment (last dose given within 10 days before randomization) with heparin therapy or oral anti coagulation.
- Gastrointestinal bleed or major surgery within 3 months.
- Planned or likely revascularization (any angioplasty or vascular surgery) within the next 3 months (if clinically indicated, vascular imaging should be performed prior to randomization whenever possible)
- Scheduled for surgery or interventional treatment requiring study drug cessation.
- Qualifying TIA or minor stroke induced by angiography or surgery.
- Severe non-cardiovascular comorbidity with life expectancy < 3 months.
- Women of childbearing age not practicing reliable contraception who do not have a documented negative pregnancy test.
- Currently receiving an investigational drug or device.

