### **7.5.2 Definition treatment discontinuation with investigational product(s)**

A patient should discontinue the study drug for any of the following reasons:

- ✓ Intercurrent condition that requires discontinuation of the study (e.g. lab abnormalities, Appendix 5).
- ✓ Positive serum pregnancy test or desire to become pregnant
- ✓ Contraception cessation

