## 6.4 剂量方案

### 第一组：

- ◇ 第 1 天\*：氯吡格雷 300mg 和公开标签的阿司匹林 75mg-300mg。
- ◇ 从第 2 天到第 21±2 天：氯吡格雷 75mg/天和阿司匹林 75mg/天。
- ◇ 从第 22±2 天随访到第 90±7 天（疗程不超过 75 天）：氯吡格雷 75mg/天和阿司匹林安慰剂 75mg/天。

\*在第 1 天给予阿司匹林的总剂量 (75mg-300mg) 包括在第 1 天内任何时间、任何地点（包括在急诊室）给予患者的阿司匹林。

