### 第二组：

- ◇ 第 1 天\*：氯吡格雷安慰剂 300 mg 和公开标签的阿司匹林 75mg-300mg。
- ◇ 从第 2 天到第 21±2 天：氯吡格雷安慰剂 75mg/天和阿司匹林 75mg/天。
- ◇ 从第 22±2 天随访到第 90±7 天（疗程不超过 75 天）：氯吡格雷安慰剂 75mg/天和阿司匹林 75mg/天。

\*在第 1 天给予阿司匹林的总剂量 (75mg-300mg) 包括在第 1 天内任何时间、任何地点（包括在急诊室）给予患者的阿司匹林。

研究药物应在随机化后 1 小时内尽快开始使用。

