### **7.5.2 明确停止应用研究药物的指征**

在下列情况下患者应停止应用研究药物:

- ✓ 要求停药的临床并发症(例如化验值异常, 见附件5)
- ✓ 妊娠试验阳性或有妊娠的愿望
- ✓ 避孕终止

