#### 9.1.2 基线期评估

基线期评估包括：患者的人口学信息、本次脑血管事件的症状、服药史、既往史、家族史、吸烟饮酒史、体检结果、治疗前 mRS。

将对筛选对象进行实验室检查：血肌酐、血糖、中性粒细胞计数、白细胞计数、血小板计数、凝血象等。

将对筛选对象进行查体：体重、生命体征（卧位收缩压/舒张压/心率）。

将使用标准化仪器记录筛选对象的脑影像学检查、心电图检查结果。

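### The Chinese final protocol's pregnancy exclusion names a positive test where the English requires a documented negative one, so as printed it does not exclude an untested woman using no contraception

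*Supplement*

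**What the plan says.** The supplement gives the final protocol in English and in Chinese.

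- **English**, synopsis and section 5.2, exclusion criteria: "Women of childbearing age not practicing reliable contraception who do not have a documented negative pregnancy test". Version 1.0 has the same wording in its synopsis and section 5.1.
- **Chinese**, synopsis and section 5.3 (排除标准): "没有采取有效的避孕措施且妊娠试验阳性记录的育龄期女性". In English: women of childbearing age who use no effective contraception and have a record of a positive pregnancy test.

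The stopping rule in section 7.5.2 fixes the meaning of 阳性. The Chinese has "妊娠试验阳性或有妊娠的愿望" where the English has "Positive serum pregnancy test or desire to become pregnant".

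On dosing, Chinese section 6.4 gives the first group, on day 1, "氯吡格雷 300mg 和公开标签的阿司匹林 75mg-300mg". The second group gets clopidogrel placebo with the same open-label aspirin range. Timing is the same for both groups: "研究药物应在随机化后 1 小时内尽快开始使用".

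**The concern.** The English criterion works as a screen. A woman of childbearing age without reliable contraception may enter only if a negative test is on file, so the site has to test her. The Chinese criterion turns on a positive result being on file. If nobody tests her there is no such result, and the sentence gives no reason to test.

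At stake are a single eligibility rule across the two texts and the safety of a small group of women. Study drug follows randomization within an hour, with aspirin in both arms and a clopidogrel loading dose in one. The remaining pregnancy provisions of the Chinese text, in sections 7.5 and 7.5.2, stop drug that has already been started; they do not keep anyone from the first dose.

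**Working it through.** The plan states no figure on this point, so the check compares the two rules case by case.

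**1. Apply each rule.** Cross contraception (yes or no) with the test on record (negative, positive, none). Two readings of the Chinese are shown. In the natural one, 没有 negates only the contraception clause. In the other, it is stretched over both halves of the sentence.

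| Contraception | Test on record | English | Chinese, natural reading | Chinese, 没有 over both halves | Proposed Chinese |
|---|---|---|---|---|---|
| no | none | excluded | **not excluded** | excluded | excluded |
| no | positive | excluded | excluded | **not excluded** | excluded |
| no | negative | not excluded | not excluded | **excluded** | not excluded |
| yes | any | not excluded | not excluded | not excluded | not excluded |

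The natural reading differs from the English in one situation and the stretched reading in two. Neither reproduces the English rule while 阳性 stands. The proposed wording differs in none.

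**2. Is it an amendment?** No. The English wording is the same in version 1.0 and the final version. The English log (1.0 to 1.1, 1.1 to 1.2, 1.2 to 1.3) and the Chinese log for the same steps deal with the aspirin period, visits, sample size, subgroups, number of centers and concomitant drugs. No entry touches eligibility.

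**3. Does anything else close the gap before dosing?** The Chinese schedule of assessments (section 1.2) lists no pregnancy test. The baseline laboratory list in section 9.1.2 reads "将对筛选对象进行实验室检查：血肌酐、血糖、中性粒细胞计数、白细胞计数、血小板计数、凝血象等"; its closing 等 leaves the list open, but a pregnancy test is not named. No other Chinese entry criterion covers an untested woman.

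**4. How many women?** The documents give no fraction, so this is assumption only. Suppose 0.02% to 0.5% of the 5,100 participants are untested women of childbearing age using no contraception:

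- 5,100 × 0.0002 = 1.02
- 5,100 × 0.005 = 25.5
- allocated to clopidogrel at 1:1: 1.02 / 2 = 0.51 to 25.5 / 2 = 12.75

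That is about 1 to 26 women, of whom roughly 0.5 to 13 would receive the clopidogrel load.

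**5. Primary analysis.** Patients who stop study drug are followed to the scheduled end (protocol 7.5.3) and stay in the intent-to-treat population if they were randomized and dosed (SAP, Intent-to-Treat Population). A handful of such women does not materially alter power or the hazard ratio.

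**The case against.** Four points can be made on the other side.

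- **The harm depends on how the sentence is read.** The second half of the Chinese phrase has no verb, and the natural reading supplies one. If 没有 governs both halves, the untested woman is excluded. This is a fair limit on certainty about the exact harm. It does not rescue the text, because that reading lets in a woman with a positive test.
- **It may be one misread character.** 阳 and 阴 look alike, and the text was extracted from PDF by a program. With 阴性 printed and 没有 spanning both halves, the sentence would give the English rule. A misread cannot be fully ruled out without the page image, but the same wording appears in two separate places, which makes it unlikely. Even with 阴性, the sentence could be read as excluding women who have a negative record, so the second half needs its own negation.
- **The practical contrast is thin.** Neither language schedules a baseline pregnancy test, and both admit women using contraception without one. Entry is at 40 or older, sites are certified on eligibility (section 4.4), and the stopping rules make clear that pregnancy and study drug do not go together. All this stands and bears on the weight. Training may catch the slip, but it does not replace a correct written criterion, and the documents do not say which language governs.
- **The head count is not evidence.** Agreed. The range is 25-fold wide and rests on chosen inputs, so it should carry no weight in judging how serious the point is.

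**Conclusion.** The discrepancy is real and should be corrected. The Chinese exclusion, printed identically in the synopsis and section 5.3, does not state the English rule on any reading. On the natural one it leaves eligible the untested woman without contraception whom the English excludes. The mismatch itself is certain from the printed text. That it is a translation slip, and that the English is the intended rule, are inferences from the unchanged English wording and the silence of both amendment logs.

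The practical effect is probably very small. It is a matter of participant safety and of a consistent entry criterion, with no material consequence for power or the primary analysis.

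**What to change.** In the exclusion criteria of the Chinese synopsis and of Chinese section 5.3, replace the phrase with:

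未采取有效避孕措施且无妊娠试验阴性记录的育龄期女性

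This excludes women of childbearing age with no effective contraception and no documented negative pregnancy test. It matches the English, and because each half carries its own negation the ambiguity of reading goes as well.

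The cost is one phrase in two places. The English text stays as it is, no visit is added, and no test is needed beyond what the English rule already calls for.

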## 6 治疗方案

### 6.1 研究药物

本随机、双盲研究的主要目的是比较氯吡格雷与阿司匹林联合应用，之后单独应用氯吡格雷组与单独使用阿司匹林组疗效的差异。研究使用的两种氯吡格雷片剂（75mg 有效的氯吡格雷和氯吡格雷安慰剂）是难以辨别的（其大小、形状、颜色、外观完全相同）。

在本研究中，药物的轻微副作用是不常见的，因此，受试者或研究者不可能通过副作用来区分安慰剂与活性药物。而且分中心使用的生物学实验没有揭盲的可能。

研究者不能揭盲随机码（治疗码），除非出现特殊情况。例如，发生严重不良事件（SAE）时，公开研究药物信息对治疗受试者非常重要的情况下，才可以揭盲研究药物。

### 6.2 药品规格

- ◇ 氯吡格雷，每片 75mg；
- ◇ 氯吡格雷安慰剂，每片 75mg
- ◇ 阿司匹林，每片 75mg；
- ◇ 阿司匹林安慰剂，每片 75mg。

## 6.3 给药方式

- ◇ 口服

## 6.4 剂量方案

### 第一组：

- ◇ 第 1 天\*：氯吡格雷 300mg 和公开标签的阿司匹林 75mg-300mg。
- ◇ 从第 2 天到第 21±2 天：氯吡格雷 75mg/天和阿司匹林 75mg/天。
- ◇ 从第 22±2 天随访到第 90±7 天（疗程不超过 75 天）：氯吡格雷 75mg/天和阿司匹林安慰剂 75mg/天。

\*在第 1 天给予阿司匹林的总剂量 (75mg-300mg) 包括在第 1 天内任何时间、任何地点（包括在急诊室）给予患者的阿司匹林。

### 第二组：

- ◇ 第 1 天\*：氯吡格雷安慰剂 300 mg 和公开标签的阿司匹林 75mg-300mg。
- ◇ 从第 2 天到第 21±2 天：氯吡格雷安慰剂 75mg/天和阿司匹林 75mg/天。
- ◇ 从第 22±2 天随访到第 90±7 天（疗程不超过 75 天）：氯吡格雷安慰剂 75mg/天和阿司匹林 75mg/天。

\*在第 1 天给予阿司匹林的总剂量 (75mg-300mg) 包括在第 1 天内任何时间、任何地点（包括在急诊室）给予患者的阿司匹林。

研究药物应在随机化后 1 小时内尽快开始使用。

## 7 研究药物处理

### 7.1 药物提供与储存

赛诺菲-安万特公司提供该项双盲研究使用的药物（研究药物与安慰剂）。研究药物将被贮存在安全的地方，由研究者或其他授权人员直接负责管理，并按照标签所描述的条件进行储存。

### 7.2 包装和标签

每个患者的药盒均要根据患者的随机号进行标注

根据研究和访视周期的设计，研究药物包装为公用药盒和患者药盒两个药盒。其中患者药盒内含两个小药盒，每个小药盒中又分为两部分（两袋）。具体如下：

公用药盒：内含公开标签的阿司匹林（用“A0”表示）。

包装分为两种规格：第一种规格为 50mg/片，12 片/板，共 15 板，以及 25mg/片，30 片/板，共 1 板，用于第 1 天。

一个公共药盒中的阿司匹林可供 30 个患者使用。

患者药盒：包括小药盒 1 和小药盒 2。

小药盒 1 有 2 个药袋：一袋是非公开标签的氯吡格雷或氯吡格雷安慰剂：75mg/片，7 片/板，4 板，用于第 1 天到第 21 ± 2 天。另一袋是非公开标签的阿斯匹林：25mg/片，30 片/板，2 板+6 片，用于第 2 天到第 21 ± 2 天。

小药盒 2 有 2 个药袋：一袋是非公开标签的氯吡格雷或氯吡格雷安慰剂：75mg/片，7 片/板，11 板。另一袋是非公开标签的阿斯匹林或阿斯匹林安慰剂：25mg/片，30 片/板，8 板。均用于第 21 ± 2 天到 90 ± 7 天。

标签的内容将符合当地的管理规范与要求

### 7.3 职责

研究者、医院的药剂师或其他储存和分发药物的人员应确保在临床实验中使用的研究药物按照申办方的要求进行

安全保管和使用，并遵循现有规章制度。

所有的研究药物将根据研究者的处方进行分发，研究者有责任保证正确记录研究药物的分发和回收。

在研究药物接收和使用中出现的任何质量问题(如：研究药物在外观、标签、有效天期等方面的缺损)应该及时向申办方汇报。

在任何情况下研究者均不能向第三方提供研究药物。除按临床试验方案要求进行使用外，研究药物不能通过任何方式使用和处理。

## 7.4 伴随治疗

### 7.4.1 禁忌的伴随用药

在研究过程中使用以下药物是违背方案的。但是如果临床需要，则主治医生将需要慎重考虑使用这些干预措施。

- ◇ 标签公开的阿司匹林(除第 1 天外)；
- ◇ 非甾体抗炎药，Cox1 和 Cox2 抑制剂。如果绝对需要，非甾体抗炎药服用时间应小于 5 天，并且开始使用时间不早于随机化分组的第 8 天；
- ◇ 标签公开的噻吩吡啶(噻氯吡啶，氯吡格雷)；
- ◇ 双嘧达莫；
- ◇ 所有肝素类药物；
- ◇ 口服抗凝药物；
- ◇ IIb/IIIa受体拮抗剂；
- ◇ 溶栓药物；
- ◇ 血管干预措施(血管外科手术和/或任何血管成形术)。

如果在随机化后的 3 个月内绝对需要此类干预措施，研究药物应在干预实施 5 天前停止使用。除非患者需要服用

公开标签的氯吡格雷或阿司匹林，研究治疗将立即重新启动。在这种情况下，只有当公开标签的抗血小板治疗结束后，研究药物才可以被重新启动。

#### **7.4.2 允许的伴随用药**

除以上列出的药物单之外的任何用药(包括抗高血压药物)都是允许的。若对患者有必要，研究者慎重考虑后应尽可能给予患者稳定的剂量。由于不确定泵抑制剂（如奥美拉唑等）与氯吡格雷药物之间存在相互影响，因此既往服用质子泵抑制剂的患者应使用其他药物进行替换（如 H2 受体抑制剂），需要治疗的患者应优先使用 H2 受体抑制剂等药物而尽量避免使用质子泵抑制剂。同样，与氯吡格雷有相互作用的药物都应该尽量避免使用，这些药物包括：艾美拉唑（耐信）、西咪替丁（包括处方和非处方药物）、氟康唑（大扶康）、酮康唑（里素劳片）、伏立康唑（威凡）、依曲韦林、非尔氨酯、氟西汀（百优解，奥氮平氟西汀）、氟伏沙明（兰释）

研究期间，任何在随机化前进行的治疗和/或开立的处方或研究过程中的任何用药改变都应记录在病例报告表中。

#### **7.4.3 治疗依从性和可靠性**

- ◇ 患者的依从性通过每次随访时计算回收药片的数量来进行评估。
- ◇ 研究者（或代表）应完成病例报告表中的相应页和研究药物记录表格。
- ◇ 必须记录研究药物中断的天数。

#### **7.5 患者暂时停药、永久停药或失访的处理方案**

- ◇ 研究药物应尽可能持续使用。如果停用研究药物，应该判断是否能暂时停药；永久停药是最后的方式。任何停药均应完整记录在 CRF 的相应页面上。在任何情况下，患者应尽可能长的参加试验。
- ◇ 在任何情况下，妊娠都将导致永久性停止试验。

### **7.5.1 暂时停止应用研究药物**

一旦研究者根据其最佳临床或实验室监测判断(见附表 5)认为研究药物不太可能与发生的事件相关, 且在没有任何他继续研究禁忌的情况下, 应重新服用药物。重新服用药物应该在严密合理的监测下进行。

如果确定可以重新开始试验, 研究人员应将所有暂时性试验中止(小于10天)重新开始的时间记录在CRF的相应页面上。

### **7.5.2 明确停止应用研究药物的指征**

在下列情况下患者应停止应用研究药物:

- ✓ 要求停药的临床并发症(例如化验值异常, 见附件5)
- ✓ 妊娠试验阳性或有妊娠的愿望
- ✓ 避孕终止

### **7.5.3 对永久停止用药患者的处理方案**

- ✓ 对患者的随访应遵照研究方案特殊说明的程序, 持续到研究方案预定的研究结束时间, 或患者从不良事件中恢复到正常或病情稳定的时间(二者取较长的时间)。
- ✓ 研究者应将所有确定的中途退组记录在CRF的相应页面上。
- ✓ 所有在最后一次随访前停止使用研究药物的患者应该在3个月时完成终点随访。
- ✓ 对于失访的患者, 其CRF均应记录到最后一次随访。研究者应尽最大努力与每个患者联系, 确定患者失访的原因并判断其健康状况。

### **7.5.4 结局**

- ✓ 已经从研究中撤出的患者不能再进入研究。该患者的随机码和治疗药物将不能继续使用。

- ✓ 研究者应与申办方联系共同确认中断治疗和/或患者的撤出。
- ✓ 已随机化的患者将不会被取代。

### **7.5.5 研究药品的回收和销毁**

- ✓ 研究者（或药剂师）应建立回收研究药物的详细记录，研究者和监查团队应共同确认该记录。
- ✓ 研究者不能破坏未使用或已被部分使用的研究药品，除非申办方提供书面授权。

若研究药物在质量方面存在缺陷，申办方将采取回收程序进行回收。在这种情况下，为召回研究药物和消除潜在危害，研究者有责任满足申办方提出的任何要求。

## **7.6 盲法系统和紧急揭盲程序**

### **7.6.1 盲态方式描述**

本随机、双盲研究的主要目的是比较氯吡格雷与阿司匹林联合应用，之后单独应用氯吡格雷组与单独使用阿司匹林组疗效的差异。

研究使用的两种氯吡格雷片剂（75mg有效的氯吡格雷和氯吡格雷安慰剂）是难以辨别的（其大小、形状、颜色、外观完全相同）。

研究使用的两种阿司匹林片剂（75mg 有效的阿司匹林和阿司匹林安慰剂）是难以辨别的（大小、形状、颜色、外观完全相同）。

在本研究中，分中心使用的生物学实验没有揭盲的可能。

研究者不能揭盲随机码（治疗码），除非出现特殊情况。例如，发生严重不良事件（SAE）时，公开研究药物信息对治疗受试者非常重要的情况下，才可以揭盲研究药物。

## 7.6.2 患者随机分组的方法

随机码列表将在合同研究组织（CRO）集中生成。

患者的药物将按照随机码表进行包装。在治疗期间，患者将接受氯吡格雷/阿司匹林组或者阿司匹林组的研究药物治疗，分配到两组的随机概率为1:1。

将根据随机化时发病时间是否超过12小时进行分层随机分组。

在第一天(基线随访)时随机顺序表将由计算机系统自动生成，受试者将按照入组的先后顺序，由小到大依次获得指定的随机试验药物编号，之后研究者将给患者与号码相应的药物。根据各中心的研究进展，可调配入选的病例数，但需要得到数据管理中心的确认。

## 7.6.3 研究过程中的紧急破盲

如果出现不良事件（AE），在特殊的情况下，即当了解药物成分对患者的治疗十分必要时，才能够进行破盲。如果可能，研究者在破盲前应该与监查团队联系。

如果研究分中心的研究者认为有必要破盲，他/她必须立即通知该分中心负责人，并在分中心负责人同意后尽快通知监察员和申办方。所有的电话将由CRO记录。

如果破盲，研究者应书面记录破盲天期、时间和原因，研究药物将停止使用。

# 8 患者安全

## 8.1 不良事件监测

所有不良事件将遵循相应法规进行处理和报告，其报告将包括在最终的临床试验报告中。

## 8.2 不良事件(AE)和严重不良事件(SAE)定义

**不良事件**是指受试者因服用研究药物或在研究中发生的任何医源性不利事件，无论是否与服用研究药物或治疗过

程有因果关系。

除了因为事件的过程、严重性或其他特征，研究者根据他的最佳临床判断，认为在这种临床情况下该事件应被考虑为例外事件时，终点事件不被考虑为不良事件。

**严重不良事件**是服用任何剂量药物出现的不良事件

- 死亡
- 威胁生命的

备注：危及生命，其严重程度的定义是指事件发生当时将危及患者生命，而非假设事件如果更严重时将导致患者死亡。

- 需要住院治疗或是延长住院时间
- 导致永久性或严重残障
- 先天性的缺陷或出生缺陷
- 重大医源性事件

在其它情况下，应运用医学和科学的决策来判断迅速上报是否合适。例如某事件可能并不威胁生命、导致死亡或需要住院治疗，但是有可能对患者造成危害，或是需要干预以预防定义中描述的不良后果，则该事件被认为是严重不良事件，需要迅速上报。

这些通常被认为是严重的事件。

备注：例如：在急诊室/家中的对过敏性支气管痉挛的强化治疗、血液病、惊厥或无症状的ALT升高 $\geq 10$ 单位，虽然并不导致住院，药物依赖或滥用，也应被视为严重不良事件。

## **8.3 研究者在安全性报告方面的职责**

### **8.3.1 不良事件**

任何不良事件，不论其严重程度如何，是否与研究药物相关，从临床研究方案第一天访视或签署知情同意书（例如出现在洗脱期）后开始，到研究方案计划的最后一次随访结束为止，都应记录在病例报告表里的相应页面。在任何可能的情况下，患者出现的症状都应被分组为某个单独的综合征或临床诊断。研究者应具体描述事件发生的时间、事件强度、对研究药物采取的相应措施、给予的对症治疗、结局以及他/她关于该不良事件是否有可能由研究药物导致的判断。

如果化验检查，生命体征或心电图异常与研究药物之间具有医学相关性：例如出现临床症状、需要对症治疗、导致停药和/或严重后果，它们将被作为不良事件记录。

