## **8.2 Definitions of Adverse Event (AE) and Serious Adverse Event (SAE)**

An **Adverse Event** is any untoward medical occurrence in a patient or clinical investigation patient administered a pharmaceutical product and which does not necessarily have to have a causal relationship with this treatment.

Efficacy endpoints will not be considered as AEs except if, because of the course or severity or any other features of such events, the Investigator, according to his/her best medical judgment, considers these events as exceptional in this medical condition.

A **Serious Adverse Event** is any untoward medical occurrence that at any dose:

- ✓ Results in death, or
- ✓ Is life-threatening, or

Note: The term "life-threatening" in the definition of "serious" refers to an event in which the patient was at risk of death at the time of the event; it does not refer to an event which hypothetically might have caused death if it were more severe.

- ✓ Requires inpatient hospitalization or prolongation of existing hospitalization, or
- ✓ Results in persistent or significant disability/incapacity, or
- ✓ Is a congenital anomaly/birth defect, or
- ✓ Is a medically important event

Medical and scientific judgment should be exercised in deciding whether expedited reporting is appropriate in other situations, such as important medical events that may not be immediately life-threatening or result in death or hospitalization but may jeopardize the patient or may require intervention to prevent one of the other outcomes listed in the definition above.

These should also usually be considered serious.

Note: Examples of such events are intensive treatment in an emergency room or at home for allergic bronchospasm, blood dyscrasias, convulsions or asymptomatic ALT increase  $\geq 10$  ULN that does not result in hospitalization, or development of drug dependency or drug abuse.

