### **8.3 Obligation of the investigator regarding safety reporting**

#### **8.3.1 Adverse Events**

All Adverse Events regardless of seriousness or relationship to Investigational Product, spanning the time from the first visit planned in the Clinical Trial Protocol/signature of the informed consent (i.e., occurring during the washout period) to the last visit planned in the protocol, are to be recorded on the corresponding page(s) included in the Case Report Form. Whenever possible, symptoms should be grouped as a single syndrome or diagnosis. The Investigator should specify the date of onset, intensity, action taken with respect to Investigational Product, corrective treatment/therapy given, outcome and his/her opinion as to whether there is a reasonable possibility that the Adverse Event was caused by the Investigational Product.

Laboratory, vital signs or ECG abnormalities are to be recorded as Adverse Events only if they are medically relevant: symptomatic, requiring corrective treatment, leading to discontinuation and/or fulfilling a seriousness criterion.

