#### **8.3.2 Serious Adverse Events**

In the case of a Serious Adverse Event the Investigator must immediately:

SEND (within 1 working day, preferably by fax) the signed and dated corresponding page(s) in the Case Report Form to the representative of the Monitoring Team whose name, address and fax number appear on the Clinical Trial Protocol;

ATTACH a photocopy of all examinations carried out and the dates on which these examinations were performed. Care should be taken to ensure that the patient's identity is protected and the patient's identifiers in the Clinical Trial are properly noted on any copy of source documents provided to the Sponsor. For laboratory results, include the laboratory normal ranges;

Follow-up of any Serious Adverse Event that is fatal or life threatening should be provided within one additional calendar week.

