### **8.3.2 严重不良事件**

对于严重不良事件，研究者必须立即采取行动：

立即通知申办方的相应负责人，发送有签字和天期的病例报告表中的相应页给申办方的相应负责人，附加所有检查的复印件和这些检查完成的天期。应确保患者隐私得到保护，确保在提供给申办方的临床原始资料的复印件中去除患者的身份信息。实验室结果应包括正常范围值。

对任何严重不良事件的随访应该在该事件发生后一周内完成。并将严重不良事件填写在 CRF 相应位置，签字后最好以传真的方式报告给监测中心，监测中心的名称，地址，传真号将在临床试验方案中注明。

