### **8.3.3 随访**

研究者应采取所有合理的措施来确保患者的安全。研究者应该追踪任何有关不良事件的结果（临床症状、体征、实验室检查结果等），直到患者恢复正常或病情稳定。

如果出现任何严重不良事件，研究者应追踪患者，直到临床症状完全缓解且实验结果恢复正常或直到病情稳定后。

这意味着在患者退出临床试验后随访仍将继续。监查团队有可能要求额外的研究。

在研究药物终止后，研究者应注意任何时间出现的任何严重不良事件。

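### The final Chinese and English protocols give different rules for recording adverse events and serious adverse events, and neither version is named as governing

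*Supplement*

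**What the plan says.** The supplement contains a final protocol in English and a final protocol in Chinese. Three safety rules differ between them.

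- **ALT example of a serious event (Section 8.2).** English: "asymptomatic ALT increase $\geq 10$ ULN that does not result in hospitalization". Chinese: "惊厥或无症状的ALT升高 $\geq 10$ 单位", that is, an asymptomatic rise of at least ten units. The Chinese note adds that such events should be regarded as SAEs.
- **Laboratory, vital-sign and ECG abnormalities (Section 8.3.1).** English: "Laboratory, vital signs or ECG abnormalities are to be recorded as Adverse Events only if they are medically relevant", followed by four criteria (symptoms, corrective treatment, discontinuation, seriousness). Chinese: "如果化验检查，生命体征或心电图异常与研究药物之间具有医学相关性", a condition that the abnormality be medically related to the study drug, followed by similar criteria given as examples.
- **Follow-up of serious events (Section 8.3.2).** The English asks for follow-up of fatal or life-threatening SAEs within one additional calendar week. Chinese: "对任何严重不良事件的随访应该在该事件发生后一周内完成", meaning that follow-up of any SAE is to be completed within a week of the event. Chinese Section 8.3.3 says instead "研究者应追踪患者，直到临床症状完全缓解且实验结果恢复正常或直到病情稳定后", meaning until recovery with normal laboratory results, or until stabilization.

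The SAP (Safety Endpoint) defines the incidence of AEs and SAEs by reference to the protocol and names no language version. The SAP (Interim Analyses) has an independent statistician prepare unblinded SAE summaries for the DSMB. Protocol Section 4.1 places the roughly 100 centers in China.

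**The concern.** AEs and SAEs are a secondary safety endpoint (Section 4.6.3.4). The named safety objectives in Section 3.2.5 include thrombotic thrombocytopenic purpura, granulocytopenia and renal failure, all of which rest heavily on laboratory findings. If two current texts tell investigators different things about what to record and what counts as serious, the same event can be handled differently at two sites.

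The differences pull in opposite directions. The Chinese ALT wording would turn trivial changes into SAEs. The Chinese laboratory wording could lead a blinded investigator who doubts a drug cause to leave out a relevant abnormality. Neither effect favors an arm by itself, because the wording is the same for both. But spurious SAEs added equally to both arms dilute a real contrast, and omitted events are simply lost. The SAE summaries are a main input to the DSMB, the body that sees unblinded safety data.

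**Working it through.** The plan has no figure to reproduce here. The check sets the two texts side by side and includes one small illustration.

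**1. ALT threshold.** The documents give no upper limit of normal (ULN) for ALT, so assume 35 to 50 U/L.

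- English: 10 × ULN = 10 × 35 = 350 U/L, up to 10 × 50 = 500 U/L.
- Chinese: a rise of 10 units, for example 20 + 10 = 30 U/L, which is below even the lower assumed limit of 35.
- Ratio: 350 / 10 = 35, up to 500 / 10 = 50.

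The Chinese protocol elsewhere expresses transaminases as multiples of normal: more than twice the upper limit in the synopsis note on severe hepatic insufficiency, and more than twice normal in Appendix 5. Ten units is out of line with that convention. It looks like a rendering slip, although the documents do not settle this.

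**2. Laboratory rule.** Three statements in the Chinese text bear on it.

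- Section 8.2 defines an AE without requiring a causal link.
- The first sentence of Section 8.3.1 requires every AE to be recorded whether or not it is related to the study drug.
- The second paragraph of Section 8.3.1 makes a relation to the study drug the condition under which laboratory, vital-sign and ECG abnormalities become AEs.

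The third conflicts with the first two, and with the English rule, which carries no relation to the drug.

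**3. SAE follow-up.** Chinese Section 8.3.2 sets one week from the event for completing follow-up of any SAE. Chinese Section 8.3.3 sets no time limit and expects follow-up to continue after the patient leaves the trial. The English one-week rule covers only fatal or life-threatening SAEs, and it does not say that follow-up ends then. The Chinese sentence therefore conflicts with its own next section and with the English.

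**4. How often it could matter.** Section 4.6.3.2 requires no specific laboratory safety tests in either language, and the Section 1.2 schedules list laboratory tests only at screening and at event visits. A post-baseline ALT change or other laboratory abnormality would therefore come to light mainly at event visits or through tests done for clinical reasons. The documents hold no ALT results, SAE counts or DSMB tables, so the effect on counts cannot be computed.

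**The case against.** The strongest reply is that these are translation inconsistencies in a few sentences and that no harm is shown. Much of it stands, and it rules out several stronger readings.

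- **That the DSMB's SAE tables are wrong.** A reader might infer this, but the documents contain no such tables. They do not say which language version governs or which one sites applied. That Chinese sites worked from the Chinese text is a reasonable inference, not a stated fact.
- **That the Chinese protocol records laboratory abnormalities only when drug-related.** It does not say so. The restrictive word is in the English sentence, not the Chinese. The Chinese section also asks for a causality opinion on each AE, which presupposes that unrelated events are recorded. The rule is self-contradictory rather than a clear filter. It also governs AE recording, so it would reach the SAE summaries only where an omitted abnormality was serious as well. The main seriousness criteria carry no causal condition.
- **That Chinese Section 4.6.3.2 repeats the error.** That passage concerns when specific action is needed, not what is recorded.
- **That the Chinese text loosens the reporting deadline.** The English has "SEND (within 1 working day, preferably by fax" as its limit. The Chinese drops that figure but requires the investigator to act immediately, which is no looser.
- **That a given share of abnormalities goes unrecorded.** The documents give no basis for any percentage.

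It is also true that both arms are affected alike, that the primary efficacy endpoint is untouched, and that bleeding and mortality are separate safety endpoints. None of this removes the conflicts. An investigator who follows the Chinese ALT note as written would class a within-normal change as serious, and one who follows Chinese Section 8.3.1 meets two incompatible instructions.

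**Conclusion.** The point holds as a conflict between current texts that should be resolved. Three operative safety rules differ between the final Chinese and English protocols, and the Chinese text contradicts itself on two of them (recording of laboratory abnormalities and length of SAE follow-up). The SAP relies on the protocol without saying which version it means.

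The ALT discrepancy is the largest in size: 350 to 500 U/L against a 10 U/L rise, on an assumed upper limit of 35 to 50 U/L. The consequence is a risk of inconsistent AE and SAE recording, and through it inconsistent SAE summaries for the DSMB. It is not a demonstrated error in any table. Its frequency is limited by the sparse laboratory schedule. Nothing in the documents suggests that it would favor one arm.

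**What to change.** 1. Amend the Chinese Sections 8.2, 8.3.1 and 8.3.2 to agree with the English. State the ALT example as a multiple of the upper limit of normal, remove the causal condition from recording laboratory, vital-sign and ECG abnormalities, and make the one-week wording consistent with Section 8.3.3.
2. State in the protocol which language version governs, and refer to that version in the SAP where AEs and SAEs are defined.
3. Send sites a short memo on the corrected rules.
4. Within planned monitoring visits, check any SAE that rests only on the ALT example, and any recorded laboratory abnormality left out as unrelated.

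The cost is a text amendment, a memo and a small check within existing monitoring. No design feature, sample size or primary analysis changes.
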